7.6 Subject Population(s) for Analysis

Both the incidence of adverse effects and ASL evidence of hippocampal target engagement will be analyzed in all participants who receive study drug. The primary efficacy outcome measure for this trial are described above in section 3.2.

The modified Intent-to-Treat (mITT) population will include all randomized subjects who receive one dose of levetiracetam and at least one evaluation post baseline.

8 Safety and Adverse Events

8.1 Definitions

Unanticipated Problems Involving Risk to Subjects or Others

Any incident, experience, or outcome that meets all of the following criteria:

- Unexpected in nature, severity, or frequency (i.e. not described in study-related documents such as the IRB-approved protocol or consent form, the investigators brochure, etc.)
- Related or possibly related to participation in the research (i.e. possibly related means there is a reasonable possibility that the incident experience, or outcome may have been caused by the procedures involved in the research)
- Suggests that the research places subjects or others at greater risk of harm (including physical, psychological, economic, or social harm).

Adverse Event

An **adverse event** (AE) is any symptom, sign, illness or experience that develops or worsens in severity during the course of the study. Intercurrent illnesses or injuries should be regarded as adverse events. Abnormal results of diagnostic procedures are considered to be adverse events if the abnormality:

- results in study withdrawal

CONFIDENTIAL

- is associated with a serious adverse event
- is associated with clinical signs or symptoms
- leads to additional treatment or to further diagnostic tests
- is considered by the investigator to be of clinical significance

Serious Adverse Event

Adverse events are classified as serious or non-serious. A **serious adverse event** is any AE that is:

- fatal
- life-threatening
- requires or prolongs hospital stay
- results in persistent or significant disability or incapacity
- a congenital anomaly or birth defect
- an important medical event

Important medical events are those that may not be immediately life threatening, but are clearly of major clinical significance. They may jeopardize the subject, and may require intervention to prevent one of the other serious outcomes noted above. For example, drug overdose or abuse, a seizure that did not result in in-patient hospitalization or intensive treatment of bronchospasm in an emergency department would typically be considered serious.

All adverse events that do not meet any of the criteria for serious should be regarded as **non-serious adverse events**.

While adverse events will not be limited to the items assessed on the SAFTEE, a two-point increase of any item on the SAFTEE (as compared to their screening visit) will be considered an adverse event.

Adverse Event Reporting Period

The study period during which adverse events must be reported is normally defined as the period from the initiation of any study procedures to the end of the study treatment follow-up. For this study, the study treatment follow-up is defined as 30 days following the last administration of study treatment.

Preexisting Condition

A preexisting condition is one that is present at the start of the study. A preexisting condition should be recorded as an adverse event if the frequency, intensity, or the character of the condition worsens during the study period.

General Physical Examination Findings

At screening, any clinically significant abnormality should be recorded as a preexisting condition. At the end of the study, any new clinically significant findings/abnormalities that meet the definition of an adverse event must also be recorded and documented as an adverse event.

Post-study Adverse Event

All unresolved adverse events should be followed by the investigator until the events are resolved, the subject is lost to follow-up, or the adverse event is otherwise explained. At the last scheduled visit, the investigator should instruct each subject to report any subsequent event(s) that the subject, or the subject's personal physician, believes might reasonably be related to participation in this study. The investigator should notify the study sponsor of any death or adverse event occurring at any time after a subject has discontinued or terminated study participation that may reasonably

CONFIDENTIAL

be related to this study. The sponsor should also be notified if the investigator should become aware of the development of cancer or of a congenital anomaly in a subsequently conceived offspring of a subject that has participated in this study.

Abnormal Laboratory Values

A clinical laboratory abnormality should be documented as an adverse event if any one of the following conditions is met:

- The laboratory abnormality is not otherwise refuted by a repeat test to confirm the abnormality
- The abnormality suggests a disease and/or organ toxicity
- The abnormality is of a degree that requires active management; e.g. change of dose, discontinuation of the drug, more frequent follow-up assessments, further diagnostic investigation, etc.

Hospitalization, Prolonged Hospitalization or Surgery

Any adverse event that results in hospitalization or prolonged hospitalization should be documented and reported as a serious adverse event unless specifically instructed otherwise in this protocol. Any condition responsible for surgery should be documented as an adverse event if the condition meets the criteria for an adverse event.

Neither the condition, hospitalization, prolonged hospitalization, nor surgery are reported as an adverse event in the following circumstances:

- Hospitalization or prolonged hospitalization for diagnostic or elective surgical procedures for a preexisting condition. Surgery should **not** be reported as an outcome of an adverse event if the purpose of the surgery was elective or diagnostic and the outcome was uneventful.
- Hospitalization or prolonged hospitalization required to allow efficacy measurement for the study.
- Hospitalization or prolonged hospitalization for therapy of the target disease of the study, unless it is a worsening or increase in frequency of hospital admissions as judged by the clinical investigator.

Procedures to minimize additional risks:

As described, a psychiatric and medical evaluation will be completed as part of screening. Participants will be closely observed for 3 hours after their first dose of study drug. Inpatients will be monitored by the clinical staff on the unit. In the event of adverse reactions or other medical complications, an MD or NP will respond to the event and 911 will be called if needed.

We are studying a low dose of levetiracetam. The low dose is the standard starting dose which has been approved for almost 20 years and is not associated with medical complications. We will be monitoring closely for psychiatric reactions. Subjects will be contacted by telephone (for outpatients) or assessed in person (if inpatient) by the research assistant for the first 5 days after starting the study medication to affirm that they are stable using the medication safety assessment checklist. Any reports of worsening (symptoms or side effects) will be immediately (same day) shared with [name] (NYC) or [name] (Shanghai). Outpatients who report worsening of psychosis or new suicidal or aggressive ideation will be asked to come into the clinic for assessment within 24 hours.

Additionally, weekly safety assessments will be conducted for the first 4 weeks of study drug administration by the study MD or NP. These assessments include the CSSRS and the SAFTEE. The BPRS will also be conducted by a research coordinator or research assistant.

If a patient develops new suicidal or aggressive ideation or has a 20% or greater worsening in their BPRS total score, this information will be shared with the clinical team and with the Chair of the

CONFIDENTIAL

DSMB ([name]). Either the clinical team or [name] can decide to discontinue study medication. After the first four weeks participants will be assessed by a research assistant and by a study MD or NP at each study visit (weeks 6, 8, and 12) using the same safety assessments as above. The participant will be assessed during weeks 5, 7, 9, 10 and 11 by phone by the research assistant who will complete the safety assessment checklist and follow the same reporting guidelines outlined above.

To minimize risk of COVI-19 exposure, all institutional guidelines will be followed, including screening of participants and staff, social distancing and use of PPE. Whenever possible, all assessments will be performed remotely or by clinicians performing them as part routine practice.

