1.5 Research Risks & Benefits

1.5.1 Risk of Study Drug

In a randomized, placebo-controlled cross-over trial in 20 healthy subjects (mean age 29 years, range 20-49 years), levetiracetam 500 mg administered twice at an interval of 12 hours produced side effects in 50% of subjects compared to 44% with placebo and 83% with lorazepam 2 mg. Unlike lorazepam, levetiracetam 500 mg did not adversely affect cognition but, compared to placebo, was associated with somnolence (40%), balance disorder (20%), dizziness (15%) but no psychiatric adverse effects. Side effects with levetiracetam are usually mild and include: somnolence, fatigue, mood swings, headache, agitation, irritability, aggression, depression, memory loss, confusion, vomiting, abdominal pain, nausea, anorexia, pharyngitis and paresthesia. Uncommon but potentially serious side effects that occur in less than 1% of patients include: psychosis, suicidal thoughts, hypersensitivity reactions and leukopenia. In our dose-finding trial we observed mild decreased appetite in 1 of 6 participants and drowsiness in 1 of 6 participants randomized to levetiracetam 500 mg.

There is increased risk of seizures with rapid withdrawal of levetiracetam. All participants will be made aware of this risk. After the 12-week study, participants will be tapered off of the medication for 9 additional days. Participants will return within 3 days of finishing the tapering for a final visit. During the first week, participants in the levetiracetam arm will have their dose lowered to 250 mg levetiracetam AM and 500 mg levetiracetam PM for 3 days, then 250 mg twice daily for 3 days, and then 250 mgs once daily for three days. The tapering regimen will be provided in a blister pack to the research participants. Participants in the placebo arm will also receive a blister pack with placebo pills. Participants who choose to withdraw from the study early (after more than 7 days of medication administration) will be reminded of this risk and will be asked to return for two visits. The first will consist of a clinical assessment and dispensation of the tapering regimen. The second visit (within 3 days of completing the tapering regimen) will consist of an abbreviated clinical assessment and study termination form.

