3.1 General Design

This is a Phase 2, multi-center, randomized, double-blind, placebo-controlled study. The study consists of an up to 4-week Screening period, one Baseline visit, weekly visits on Weeks 2-4, and then bi-weekly visits (weeks 6,8) and a week 12 visit. Additionally, there will be 1 additional follow up visit after Week 12 after the participants complete the tapering regimen. The Screening visit and Baseline visit may occur on the same day.

Screening, Visit 1	Baseline	Week 2	Week 3	Week 4	Week 6	Week 8	Week 12	Follow-Up
Days -28 to 0	Day 1	Day 6 - 10	Day 13 - 17	Day 20 - 24	Day 34- 38	Day 48- 52	Day 76 – 80	Day 85 - 93

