4.7 Early Withdrawal of Subjects

Participants will be advised verbally and in the ICF that they have the right to withdraw from the study at any time without prejudice or loss of benefits to which they are otherwise entitled. Participants may withdraw from the study at any time and for any reason and are not obligated to provide the reason.

The Investigator may discontinue a patient from the study in the event of an inter-current illness, AE, other reasons concerning the health or well-being of the patient, or in the case of lack of cooperation, non-compliance, protocol violation, or other administrative reasons. If a patient does not return for a scheduled visit, every effort should be made to contact the patient. In any circumstance, every effort should be made to document patient outcome, if possible. The Investigator should inquire about the reason for withdrawal and follow-up with the patient regarding any unresolved AEs.

Participants choosing to withdraw from the study early will be asked to return for 2 additional study visits as outlined above and will be provided the 9-day study drug tapering blister-pack and warned of the risk of seizures with abrupt discontinuation. The first visit will consist of a clinical assessment (consisting of Assessments in the Week 12 visit) and dispensation of the tapering regimen. The second visit (completed within 3 days of completing the tapering regimen) will consist of an abbreviated clinical assessment and study termination form (see Appendix: Follow up visit).

Any reason for withdrawal given (or the failure to provide a reason) must be recorded in the source documentation and on the patient's electronic case report form (eCRF).

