6.5 Follow-up Visits

Over the 12 weeks of medication administration and 9-day drug taper, participants will complete follow up assessments as outlined in the Appendix 1. The full assessment battery administered at the baseline visit will be repeated at weeks 6 and 12 or end of study participation. The optional MRI will be repeated at week 12 or end of study participation. Safety assessments by a study MD or NP and administration of the CSSRS and SAFTEE will occur weekly for the first 4 weeks and then at weeks 6, 8, and 12 weeks. The BPRS, SANS, and CGI will be repeated at weeks 2, 3, 4, 6, 8, and 12.

All participants will complete a tapering regimen (9 days) either after study completion (Week 12) or upon decision to withdraw from the study. Participants completing Week 12 will be given the tapering regimen (blister pack) and be asked to return for one final visit within 3 days of completing their tapering regimen. Participants choosing to withdraw early from the study will be asked to return for two subsequent visits: one to receive the tapering regimen, and a second within 3 days of completing the tapering regimen.

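### The adverse-event period runs to 30 days after the last dose, but the last scheduled contact is within 3 days of the taper, and the C-SSRS and BPRS are not scheduled after Week 12

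*Protocol*

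**What the plan says.** **Reporting period.** Section 8.1 defines the time during which adverse events must be reported as "the period from the initiation of any study procedures to the end of the study treatment follow-up", and adds that "the study treatment follow-up is defined as 30 days following the last administration of study treatment". Section 8.2 requires all events in the study period to be recorded, and requires the investigator to ask about them with the SAFTEE at each contact.

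**End of dosing.** Section 1.5.1 states that after the 12 weeks "participants will be tapered off of the medication for 9 additional days". Section 4.7 describes the taper pack as study drug, so the last administration is the last taper dose.

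**Contacts after Week 12.** Section 3.1 says "there will be 1 additional follow up visit after Week 12 after the participants complete the tapering regimen". Under section 6.5, completers will "be asked to return for one final visit within 3 days of completing their tapering regimen". For early withdrawals, section 4.7 says: "The second visit (completed within 3 days of completing the tapering regimen) will consist of an abbreviated clinical assessment and study termination form". The safety telephone checks in section 8.1 fall in weeks 5, 7, 9, 10 and 11.

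**Content of the Follow-Up visit.** In Appendix 1 the Follow-Up column (Day 85-93) marks vital signs, CGI, SAFTEE, Adverse Event Form and Study Completion Form. The C-SSRS and BPRS rows are marked from Screening to Week 12 and are blank at Follow-Up.

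**After the last visit.** Section 8.1 has participants told to report later events that they or their own physician believe may be related. It also has unresolved events followed, and has the sponsor notified of later deaths or events that may be related.

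**The concern.** The protocol fixes a 30-day post-treatment period but schedules almost nothing inside it. Section 8.2 asks for all events, found by active questioning. After the last visit, what remains is a narrower rule that depends on someone judging an event to be related and volunteering it.

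This matters because section 1.5.1 names seizures on rapid withdrawal as a risk and lists psychosis and suicidal thoughts among the uncommon but serious effects. Section 7.6 analyses adverse-effect incidence in everyone who receives study drug, and section 8.5.1 sends safety data to the DSMB. A count labelled as covering 30 days after the last dose would mostly reflect the first 0 to 3 days plus spontaneous reports. Few late events in such a count would say little about late safety.

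A second, smaller gap concerns the taper. Section 8.1 has information passed to the clinical team and the DSMB chair "If a patient develops new suicidal or aggressive ideation or has a 20% or greater worsening in their BPRS total score". The C-SSRS and the BPRS, the trial's instruments for suicidality and for total symptom score, are last used just before the taper begins.

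**Working it through.** **Inputs**
- Week 12 visit, W: Day 76-80 (section 3.1, Appendix 1).
- Taper: 9 days (section 1.5.1).
- Final visit: g = 0 to 3 days after the taper ends (sections 4.7 and 6.5).
- Reporting period: 30 days after the last administration (section 8.1).

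**1. Reproduce the Follow-Up window.** W + 9 + g gives 76 + 9 + 0 = Day 85 to 80 + 9 + 3 = Day 92. Appendix 1 states Day 85-93, so the lower limit matches and the upper limit agrees within one day.

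**2. Last dose and end of the period.** If the first taper dose is taken on the visit day, the last is on W + 8 (Day 84-88). If it is taken the next day, the last is on W + 9 (Day 85-89). Adding 30 days, the period closes on Day 114-119.

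**3. Share of the period after the last scheduled contact** = (30 − g)/30:

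| g (days from last dose to final visit) | Days after last contact | Share |
|---|---|---|
| 0 | 30 | 100% |
| 1 | 29 | 97% |
| 2 | 28 | 93% |
| 3 | 27 | 90% |

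**4. Sensitivity**
- A Day 93 visit after a Day 89 last dose: 89 + 30 − 93 = 26 days, 26/30 = 87%. This is one day beyond the 3-day rule.
- A Day 93 visit after a Day 85 last dose: 85 + 30 − 93 = 22 days, 22/30 = 73%. This breaks the 3-day rule by more.
- If the taper were not counted as study treatment: 30 − 9 − g = 18 to 21 days, 60-70%. Section 4.7 treats the taper as study drug, so this is not the natural reading.
- Week 12 at Day 76-80 comes before 84 days have passed. If dosing ran a full 84 days before the taper, the last taper dose would fall on 84 + 9 = Day 93. A Day 85-93 visit would then be on or before the last dose, leaving 100% of the period. The dosing length and the visit days should be reconciled.

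**5. C-SSRS and BPRS.** Appendix 1 schedules neither after Week 12, so neither covers the 9 taper days or the 30 days that follow. The text of section 6.5 ("administration of the CSSRS and SAFTEE will occur weekly for the first 4 weeks and then at weeks 6, 8, and 12 weeks") is weak support on its own: it names the SAFTEE in the same list, yet Appendix 1 does schedule the SAFTEE at Follow-Up. The appendix cells carry this point.

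**The case against.** A reader might infer that section 8.1 and the visit schedule contradict each other. They do not: a reporting period may outlast the visits, and section 8.1 keeps some mechanisms running, namely self-report, the personal physician's view, follow-up of unresolved events and sponsor notification. What stands is that these reach only related or already known events, while section 8.2 asks for all of them.

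A reader might also infer that the taper goes unmonitored. That is wrong. No contact falls during the taper, but the SAFTEE at Follow-Up combines an open inquiry with a review of body systems and looks back over it.

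The missing instruments could be read as disabling the section 8.1 triggers. The ideation trigger does not depend on a C-SSRS score and could be met through the SAFTEE or clinical assessment; only the 20% limb needs the BPRS. The attached decision, whether to stop study medication, is largely moot once the drug is being withdrawn. What remains is passing on information.

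Finally, one might expect a biased comparison of arms for rebound or suicidality after stopping. Section 7 plans no such comparison. Nor should participants be assumed to be poor reporters because of an acute state: entry requires persistent symptoms on at least 8 weeks of antipsychotic treatment, and consent requires demonstrated capacity.

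**Conclusion.** The point holds as a gap in active ascertainment. At least 27 of the 30 post-treatment days (90-100% under the 3-day rule; 87% for a Day 93 visit after a Day 89 last dose) come after the last scheduled contact. This assumes that the taper counts as study treatment and that the participant tapers and attends Follow-Up. Section 1.5.1 limits the two early-withdrawal visits to those with more than 7 days of medication, while section 4.7 does not; under 1.5.1, some early withdrawals may have no post-dose visit at all.

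The share of days is a measure of where the last question falls, not of how many contacts are needed: a single retrospective call at the end would cover the period. Over the taper, adverse events are asked about, but suicidality is not asked with the C-SSRS and BPRS change cannot be computed. The documents do not support going further, to an internal contradiction, an unmonitored taper or a biased efficacy or safety comparison. The primary analysis is unaffected.

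**What to change.** In section 6.5 and Appendix 1:

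1. Add one telephone contact about 30 days after the last taper dose (about Day 114-119), using the safety checklist already used for the calls in weeks 5, 7, 9, 10 and 11. If that is not wanted, restate the section 8.1 period as ending at the Follow-Up visit, so that the reported window matches what is collected.
2. Mark the C-SSRS (Since Last Visit form) at the existing Follow-Up visit, including for early withdrawals. The BPRS could be added as an option. With its 7-day lookback, a rating g = 0 to 3 days after the last dose would reach about 7 − g = 4 to 7 of the 9 taper days.
3. Align the SAFTEE and CGI timings in section 6.5 with Appendix 1, and reconcile sections 1.5.1 and 4.7 on which early withdrawals have the two closing visits.

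The cost is a protocol amendment, one short call per participant by existing staff and a slightly longer last visit. With the call, the close for the last participant comes about 4 weeks later. No change to the clinical triggers or to the taper is proposed.

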8.2 Recording of Adverse Events

At each contact with the subject, the investigator must seek information on adverse events by specific questioning (SAFTEE) and, as appropriate, by examination. A side effect and adverse effect of the medication is defined as a 2-point increase on any given item on the SAFTEE from baseline. Information on all adverse events should be recorded immediately in the source document, and also in the appropriate adverse event module of the case report form (CRF). All clearly related signs, symptoms, and abnormal diagnostic procedures results should be recorded in the source document, though should be grouped under one diagnosis.

All adverse events occurring during the study period must be recorded. The clinical course of each event should be followed until resolution, stabilization, or until it has been determined that the study treatment or participation is not the cause. Serious adverse events that are still ongoing at the end of the study period must be followed up to determine the final outcome. Any serious adverse event that occurs after the study period and is considered to be possibly related to the study treatment or study participation should be recorded and reported immediately.

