
CONFIDENTIAL

of antipsychotic treatment. We have recently found an absence of hippocampal volume loss during 12 months after initial stabilization (mean 10.3 weeks) on antipsychotics in 65 early psychosis patients (manuscript in preparation).

Results of the preliminary (R61) dose-finding study:

We recently completed a placebo-controlled, randomized, single-dose trial comparing levetiracetam 185 mg and 500 mg administered to 20 medication-free early psychosis patients studied at NYU Langone Medical Center. Hippocampal cerebral blood flow (CBF) was measured by arterial spin labelling (ASL) performed prior to study drug administration and two hours after study drug administration. Side effects were recorded in all 20 participants, whereas hippocampal CBF measured by ASL before and after study drug administration was analyzed in 17 participants; two participants were excluded from analysis due to poor quality scans and one participant was found to not meet entry criteria based on additional diagnostic information. Compared to placebo, levetiracetam 500 mg significantly reduced hippocampal perfusion ($-6.8\% \pm 2.6$ vs $-1.9\% \pm 2.4$, $p=0.02$, effect size = 2.0); levetiracetam 185 mg did not significantly reduce hippocampal perfusion compared to placebo ($-3.3\% \pm 4.9$ vs $-1.9\% \pm 2.4$, effect size = 0.35). Neither levetiracetam 185 mg nor 500 mg significantly reduced prefrontal cortical perfusion (selected as a test of hippocampal selectivity) compared to placebo (placebo = $1.1\% \pm 2.6$, levetiracetam 185 mg = $0.6\% \pm 4.4$, levetiracetam 500 mg = $-1.3\% \pm 4.4$; $p=0.80$ and $p=0.32$, respectively). The change in hippocampal perfusion significantly correlated with blood concentrations of levetiracetam ($r=-0.51$, $p=0.04$). There were no serious adverse events. Side effects included mildly decreased appetite in one participant (16%) and increased sedation / drowsiness in one participant in the levetiracetam 500 mg group, and increased sedation / drowsiness in one participant (14%) in the levetiracetam 185 mg group; side effects were mild and the incidence of side effects did not differ between levetiracetam and placebo ($p=0.64$ Fisher's exact test). Based on these results, we have received approval from the NIMH to proceed to the R33 study using a dose of levetiracetam 500 mg bid.

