8.5.1 Data Monitoring Committee

Our existing data safety and monitoring board (DSMB) will monitor this study. The DSMB has monitored five clinical studies over the past 9 years and is comprised of a statistician and two psychiatrists with extensive experience conducting clinical trials and in participating on DSMBs. If specific risks emerge additional members with expertise in the area of the potential safety issue will be added to the DSMB. The DSMB will approve the protocol prior to initiation of the study. The DSMB will review site performance, including recruitment, subject retention, protocol violations, and data quality reports. The DSMB will receive an unblinded report of all safety data (adverse events as defined above, including change scores on the SAFTEE assessments or findings upon clinician assessment) after completion of the first 4 subjects in addition to reports for bi-annual meetings. The DSMB will also be provided copies of all communications with the IRB. The DSMB will meet prior to initiation of the study and a minimum of every six months and will be provided data regarding enrollment and side effects and a study summary prior to each meeting. The DSMB may request additional meetings as necessary to monitor safety or site performance. The information for safety monitoring of the Shanghai site is outlined below (Section 9). Dose selection and titration schedule can be adjusted by the DSMB. [name] and study staff will not attend the closed section of the DSMB meetings. Throughout the study, notification of any Serious Adverse Events (SAEs) as well as any proposed investigator-initiated changes in the protocol will be submitted to the DSMB. Based on its review of the revised protocol, the DSMB will identify the data parameters and format of the information to be regularly reported. All SAEs and adverse events will be tabulated and submitted to the IRB and DSMB in the bi-annual (every 6 months) data reports or at the time of continuing review. AEs will be reported to the IRB annually.

9 Site Management

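### Sections 8.1 and 8.2 define the counted safety event and its reference visit differently, and 7.6 uses the narrower term for the tolerability incidence

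*Protocol*

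**What the plan says.** Tolerability is one of the stated objectives (Study Summary and section 2). Four places in the protocol bear on how it would be counted.

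- **Section 8.1, general definition.** An adverse event "is any symptom, sign, illness or experience that develops or worsens in severity during the course of the study". No size threshold is attached.
- **Section 8.1, SAFTEE clause.** "While adverse events will not be limited to the items assessed on the SAFTEE", the protocol continues, "a two-point increase of any item on the SAFTEE (as compared to their screening visit) will be considered an adverse event". The two-point rise is an added trigger, measured from screening.
- **Section 8.2.** "A side effect and adverse effect of the medication is defined as a 2-point increase on any given item on the SAFTEE from baseline". Here the same rise is the definition, measured from baseline. The section also requires that "All adverse events occurring during the study period must be recorded".
- **Section 7.6.** "Both the incidence of adverse effects and ASL evidence of hippocampal target engagement will be analyzed in all participants who receive study drug". It does not say whether 8.1 or 8.2 supplies the event.

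Section 8.5.1 gives the DSMB an unblinded safety report covering "adverse events as defined above, including change scores on the SAFTEE assessments or findings upon clinician assessment", and has all adverse events tabulated for the IRB and DSMB.

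**The concern.** A condition that is sufficient in 8.1 becomes the whole definition in 8.2, and the term defined in 8.2 is the one that 7.6 puts into the analysis. A worsening of one SAFTEE point, or an event that no SAFTEE item covers, is an adverse event under 8.1 but not an adverse effect under 8.2.

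The threshold matters more here than in a trial that expects severe toxicity, because section 1.5.1 describes levetiracetam side effects as mostly mild. If the choice between definitions stays open until the data are seen, the reported incidence depends on which section the analyst follows.

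Two further defects sit in the same sentences. The two sections name different reference visits. And 8.2 attributes the score rise to the medication, although a rise on a rating scale cannot assign cause and the rule applies equally to placebo participants.

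**Working it through.** No figure in the protocol is at issue, so the main check sets the passages side by side.

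**Step 1. Which events fall between the two definitions**

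| Event | 8.1 adverse event | 8.2 adverse effect |
|---|---|---|
| SAFTEE item up by two points or more | yes | yes |
| SAFTEE item up by one point because a symptom worsened | yes, under the general definition | no |
| New or worsened problem not covered by a SAFTEE item | yes | no |
| New symptom at the mildest grade | yes | depends on the score given to mild |

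Rows 2 and 3 need no knowledge of the anchors: a one-point rise never meets a two-point rule, and an event without an item has no score to rise. Row 4 cannot be settled. Section 6.1 describes the SAFTEE as an open-ended inquiry plus a body-system review and gives no item scale. If mild is one point above absent, the symptom is missed. If it is two points above, it is counted.

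**Step 2. Which term is analysed**

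Section 7.6 speaks of *adverse effects*. Section 8.2 is the only place that defines that term; 8.1 defines *adverse event*. The literal chain therefore runs from 7.6 to the two-point rule.

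**Step 3. The reference visit**

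- Section 8.1 compares with screening; 8.2 compares with baseline.
- The screening scales in section 6.2 do not include the SAFTEE, and Appendix 1 first schedules it at baseline. Section 6.3 also lists it at baseline.
- Screening may precede baseline by up to 28 days. Unless the two visits coincide, the 8.1 comparison has no reference score.
- Participants who take the optional scan series in section 6.8 have another SAFTEE two hours after the first dose, also on the baseline day. The word baseline alone therefore does not single out the pre-dose score.

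**Step 4. Can the size be derived?**

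No, and an illustration shows why. Let p be the proportion with any side effect and f the share of those whose largest rise is one point. The two-point incidence is p × (1 − f). For p, borrow the figures for healthy volunteers in section 1.5.1 purely as an assumption: 50% on levetiracetam 500 mg and 44% on placebo.

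- Levetiracetam arm: 84 × 2/3 = 56 participants, and 56 × 0.50 = 28 with a side effect. With f = 25%, 50% or 75%, the two-point count is 28 × 0.75 = 21, 28 × 0.50 = 14 or 28 × 0.25 = 7.
- Difference with all events counted: 50 − 44 = 6 percentage points.
- f = 50% in both arms: 25 − 22 = 3 points.
- f = 75% on levetiracetam, 50% on placebo: 12.5 − 22 = −9.5 points.
- f = 25% on levetiracetam, 50% on placebo: 37.5 − 22 = 15.5 points.

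The counted incidence cannot rise under the stricter rule, but the difference between arms can shrink, reverse or grow. The protocol gives no value for f in either arm, and the volunteer study's own counting rule is not stated.

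**The case against.** The strongest reply has three parts.

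- Section 7.6 is a population paragraph. It says who is analysed, does not cite 8.2, and the protocol uses side effect and adverse effect loosely elsewhere.
- The counting rule for a safety table is commonly left to the SAP, which is not at hand.
- Nothing is lost from the record: 8.2 requires every adverse event to be recorded, and 8.5.1 has the adverse events tabulated.

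Much of this stands. Omission from the tolerability result is a possible consequence of the wording, not something that the protocol announces, and the smaller events remain available. The reply does not remove the defect, though. The finding is not that a detail is absent: the protocol states two definitions and two reference visits that disagree, and recording every event does not settle which ones are tabulated.

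A reader might go further and infer that the pilot's events would have gone uncounted under 8.2, since section 1.3 reports that "side effects were mild and the incidence of side effects did not differ between levetiracetam and placebo". The documents do not support that. The pilot's counting rule is not stated, and its mild events may already have met a two-point rule. For the same reason, non-comparability with the pilot cannot be asserted.

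**Conclusion.** The inconsistency is real, and it touches a stated objective. Read literally, 7.6 with 8.2 yields a tolerability incidence that can omit one-point worsening and events outside the SAFTEE. The 8.1 comparison with screening also lacks a scheduled reference score. Both conclusions rest on the text alone; the first also takes *adverse effects* in 7.6 to carry the meaning that 8.2 gives it.

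The size is unknown. Three stronger readings are tempting, and none is supported:

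- **Mild side effects are lost.** This depends on SAFTEE anchors that the protocol does not give.
- **The rule biases the trial towards finding good tolerability.** A stricter threshold is a different measure, and its effect on the contrast between arms can go either way. Counting how many severity steps on an assumed scale fail the rule is no substitute, because it says nothing about how many participants take each step.
- **Section 8.1 implies a one-point cut-off.** The only SAFTEE threshold in 8.1 is two points.

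**What to change.** Reconcile 7.6, 8.1 and 8.2 before unblinding:

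1. In 7.6, state that the tolerability incidence counts adverse events as defined in 8.1, by arm, in all treated participants.
2. Report SAFTEE rises of two points or more as a separate, labelled tabulation.
3. In both 8.1 and 8.2, name the pre-dose baseline SAFTEE as the single reference.
4. In 8.2, delete *of the medication* and stop using the two-point rise as the definition.

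This needs a few sentences and one more table row. The data are already scheduled, since the SAFTEE is collected at baseline and at every later visit. The downside is a higher reported incidence in both arms, because small changes unrelated to the drug will also be counted. The separate two-point tabulation lets the reader see the larger rises on their own.
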